### **Summaries of Adverse Events and Deaths**

The number and percentage of participants overall and in each arm with treatment-emergent adverse events will be tabulated by primary MedDRA System Organ Class (SOC) and preferred term (PT). The tabulation of the number of participants with treatment-emergent adverse events by severity grade and relationship to study drug also will be provided.

Participants reporting more than one adverse event for a given MedDRA PT will be counted only once for that term using the most severe grade for the severity grade table and the most related for the relationship to study drug tables. Participants reporting more than one type of event within a SOC will be counted only once for that SOC, but both PTs will be listed.

Summaries of treatment-emergent AEs (by SOC and PT) will be provided for the following:

- All TEAEs
- TAAEs of Grade 3 or above
- All treatment-related TEAEs
- Treatment-related TEAEs of Grade 3 or above
- All SAEs (including death)
- All treatment-related SAEs
- All TEAEs leading to premature discontinuation of the study drug
- TEAEs that occurred in at least 5% of subjects within any treatment group

Adverse event summaries will provide the number and percentage of subjects with treatment-emergent AEs by SOC and PT, divided by treatment group.

Adverse events will be summarised and listed first in alphabetic order of SOC and then by PT in order of descending incidence of the pooled treatment groups within each SOC.

In summaries by severity grade, the most severe grade will be used for those AEs that occurred more than once in a participant during the study.

#### **Serious adverse events (SAE)**

The proportion of participants with at least one SAE will be reported overall. Serious adverse events will be summarized and relationship between the SAE and study drug will be detailed (Table 15, Table 16).

#### **Laboratory Evaluation**

Selected laboratory data will be summarised (n, mean, SD, median, IQR, range) by study visit along with the corresponding change from Baseline/Day 1 to Post Treatment Week 12 (Table 17, Table 18, Table 19).

Depending on sample distribution, parametric or non-parametric tests can be used to compare the change in biochemical and haematological indicators over time.

The NIH DAIDS AE Grading Table Version 2.0- November 2014 will be used to grade severity.

**Table 15. Safety parameters – adverse events and treatment discontinuation**

Adverse events	Standard monitoring arm (N=XX)	Simplified monitoring arm (N = XX)
Participants reporting any TEAE up to 30 days after last dose, n (%) Grades 1-2, n (%) Grade 3, n (%) Grade 4, n (%)		
Participants reporting treatment-related TEAE up to 30 days after last dose, n (%) Grades 1-2, n (%) Grade 3, n (%) Grade 4, n (%)		
Serious TEAE, n (%)		
Treatment-related serious TEAE, n (%)		
Treatment discontinuation due to adverse event, n (%)		
Death, n (%)		
Adverse events Common (>5% of study population), n (%) Specify (list)		
Unscheduled clinic visits or phone contact, n (%)		

**Table 16. Safety parameters – adverse events and treatment discontinuation, by visit type**

Adverse events	Standard monitoring arm Phone contact (N=XXX)	Standard monitoring arm Clinic contact (N=XXX)	Simplified monitoring arm Phone contact (N = XXX)
Participants reporting any TEAE up to 30 days after last dose, n (%) Grades 1-2, n (%) Grade 3, n (%) Grade 4, n (%)			
Participants reporting treatment-related TEAE up to 30 days after last dose, n (%) Grades 1-2, n (%) Grade 3, n (%) Grade 4, n (%)			
Serious TEAE, n (%)			
Treatment-related serious TEAE, n (%)			
Treatment discontinuation due to adverse event, n (%)			
Death, n (%)			
Adverse events Common (>5% of study population), n (%) Specify (list)			

**Table 17. Listing of serious adverse events**

Study Arm	Date Onset	Date resolved	Diagnosis or event description	SAE criteria‡	Outcome§	Relationship to study drug
Standard monitoring						
Simplified monitoring						

‡ Death, hospitalised, life threatening, medically important, congenital anomaly, disability

§ Recovered, Improved, Unchanged, Worsened, Unknown, Died

**Table 18. Serious adverse events summary**

SAE – event summary	Standard monitoring N=XXX	Simplified monitoring N=XXX
N of participants experiencing any treatment-emergent SAE by MedDRA SOC and Preferred Term, n (%) SOC (alphabetical order) List PT		

**Table 19. Summary table for key laboratory evaluations – Standard monitoring arm**

Lab parameter	N	Mean	SD	Min	Q1	Median	Q3	Max
Hb								
Baseline								
Post treatment week 12								
Change in Hb								
WBC								
Baseline								
Post treatment week 12								
Change in WBC								
Plt								
Baseline								
Post treatment week 12								
Change in plt								
ALT								
Baseline								
Post treatment week 12								
Change in ALT								
AST								
Baseline								
Post treatment week 12								
Change in AST								
Bilirubin, total								
Baseline								
Post treatment week 12								
Change in bilirubin								

**Table 20. Summary table for key laboratory evaluations – Simplified monitoring arm**

Lab parameter	N	Mean	SD	Min	Q1	Median	Q3	Max
Hb								
Baseline								
Post treatment week 12								
Change in Hb								
WBC								
Baseline								
Post treatment week 12								
Change in WBC								
Plt								
Baseline								
Post treatment week 12								
Change in plt								
ALT								
Baseline								
Post treatment week 12								
Change in ALT								
AST								
Baseline								
Post treatment week 12								
Change in AST								
Bilirubin, total								
Baseline								
Post treatment week 12								
Change in bilirubin								

**Table 21. Laboratory evaluation**

Laboratory evaluation	Standard monitoring (N=XX)	Simplified monitoring (N=XX)
Haematological parameters		
Baseline Hb, g/L (mean, SD)		
Change in Hb at post-treatment week 12, g/L (mean, SD)		
Haemoglobin #, n (%) Grade 2 Grade 3 Grade 4		
Biochemical parameters		
Baseline ALT, U/L (mean, SD)		
ALT, n (%) Grade 2 (3-5x ULN) Grade ≥3 (>5x ULN)		
Change in ALT at post-treatment week 12, g/L (mean, SD)		
Baseline AST, U/L (mean, SD)		
AST, n (%) Grade 2 (3-5x ULN) Grade ≥3 (>5x ULN)		
Change in AST at post-treatment week 12, g/L (mean, SD)		
Baseline total bilirubin, mg/dl or mmol/L (mean, SD)		
Total bilirubin *, n (%) >2.5-3.0 mg/dl (43 – 51 mmol/L) >3.0 mg/dl (>51 mmol/L)		
Change in bilirubin at post-treatment week 12, g/L (mean, SD)		

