## STUDY OBJECTIVES AND DESIGN

### Study objectives

The *primary objective* of this study is:

- To compare the proportion of patients with undetectable HCV RNA (HCV RNA <LLOQ) at 12 weeks post-treatment (SVR12) following 8 weeks treatment with glecaprevir/pibrentasvir (300/120mg) in HCV treatment naïve non-cirrhosis chronic HCV patients who have received a standard versus simplified schedule of safety and virological monitoring (intention-to-treat population).

The *secondary objectives* of this study are:

- To compare the proportion of patients achieving SVR12 between those who received a standard versus simplified schedule of safety and virological monitoring, in the modified intention-to-treat population;
- To compare the proportion of patients achieving SVR12 between those who received a standard versus simplified schedule of safety and virological monitoring, in the per-protocol population;
- To evaluate the proportion adherent to treatment and study visits (on-treatment adherence and early treatment discontinuation);
- To evaluate patient reported outcomes following treatment;
- To evaluate safety and tolerability by monitoring adverse events during treatment;
- To evaluate patient treatment satisfaction;
- To evaluate the prevalence and impact of baseline resistance associated substitutions (RAS) on efficacy (SVR12);
- To evaluate cost-effectiveness of simplified monitoring;
- To evaluate immune-virological factors associated with SVR12.

The *exploratory objective* of this study is:

- To examine the provider acceptability of the simplified monitoring strategy.

Last dose of study drug refers to the last dose of glecaprevir/pibrentasvir and will be used in the definition of treatment-emergent adverse events and laboratory abnormalities, as well as the primary efficacy endpoint (SVR12).

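### SAP Table 21 mislabels the units for bilirubin and for the ALT and AST changes, and grades ALT/AST with no worsening-from-baseline rule although entry allows up to 10 x ULN

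*SAP*

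**What the plan says.** **Units.** SAP Table 21 defines two total bilirubin categories, ">2.5-3.0 mg/dl (43 – 51 mmol/L") and ">3.0 mg/dl (>51 mmol/L"). The baseline row offers the same pair of units: "Baseline total bilirubin, mg/dl or mmol/L (mean, SD"). The change row uses a third: "Change in bilirubin at post-treatment week 12, g/L (mean, SD"). Baseline ALT and AST are in U/L, but their change rows are in g/L, for example "Change in ALT at post-treatment week 12, g/L (mean, SD").

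**Grades.** The enzyme rows read "ALT, n (%) Grade 2 (3-5x ULN) Grade ≥3 (>5x ULN") and "AST, n (%) Grade 2 (3-5x ULN) Grade ≥3 (>5x ULN"). Neither row carries a footnote. The haemoglobin and bilirubin rows do: both are tied to the treatment period plus 30 days, and bilirubin alone has a note for values already raised at screening or baseline.

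**Entry and definitions.** Protocol 3.3, items 2a and 2b, excludes ALT or AST only above 10 x ULN. The SAP section on study objectives says that the last dose "will be used in the definition of treatment-emergent adverse events and laboratory abnormalities". The Adverse Events section then defines a treatment-emergent adverse event, but no section defines a treatment-emergent laboratory abnormality. The opening of the SAP Safety Analyses section sets a general window for safety data, from first dose to 30 days after last dose.

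**The concern.** A table shell is what the programmer works from. If the SI label is coded as printed, both bilirubin categories will be empty for results held in SI units, which understates raised bilirubin. The enzyme rows err in the other direction: they can present liver inflammation that was there at entry as if it had arisen on study.

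Laboratory abnormalities are a secondary endpoint in SAP Table 9. Protocol 7.1.1 keeps abnormal results out of adverse event reporting unless they lead to a clinically relevant condition. The laboratory tables are therefore the main place where a silent rise in liver enzymes would show.

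**Working it through.** **1. The bilirubin label, from the printed pairs alone.** Molar mass = mass concentration / molar concentration.

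| Printed pair | If mmol/L | If micromol/L |
|---|---|---|
| 2.5 mg/dL (25 mg/L) and 43 | 25/43 = 0.58 g/mol | 581 g/mol |
| 3.0 mg/dL (30 mg/L) and 51 | 30/51 = 0.59 g/mol | 588 g/mol |

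A molar mass below 1 g/mol is less than that of a hydrogen atom, so mmol/L is impossible. In micromol/L the two pairs agree to within rounding.

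**2. The same check with a molar mass.** The documents give none. Assume 584.7 g/mol, range 580-590.

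- 25 mg/L / 584.7 g/mol = 42.8 micromol/L (42.4-43.1).
- 30 mg/L / 584.7 g/mol = 51.3 micromol/L (50.8-51.7).
- Taken literally, 51 mmol/L x 584.7 g/mol = 29.8 g/L, or about 2,980 mg/dL (2,958-3,009). That is roughly 1000 times the 3.0 mg/dL beside it.

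The numerals 43 and 51 are reproduced in micromol/L. Only the unit is wrong.

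**3. The change rows.** ALT and AST are measured as activity (U/L), so a change cannot be in g/L. Haemoglobin, higher in the same table, is in g/L, and the label was probably carried down from there. Bilirubin ends with three unit labels in one table. SAP Tables 19 and 20 print no units and so do not resolve this.

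**4. Who could be counted in the ALT/AST rows without having worsened.**

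- Entry is allowed up to 10 x ULN and Grade 3 or more starts above 5 x ULN, so any eligible participant above 5 x ULN at entry already meets the Grade 3 criterion before dosing.
- The SAP section on analysis windows assigns the last value on or before the first dose date to baseline. The entry value alone should therefore not be counted; a later value inside the safety window must also be raised.
- Standard arm: liver tests at weeks 4 and 8 fall inside that window.
- Simplified arm: the Protocol schedule has liver tests only at screening, baseline and week 20. The SAP post-treatment window opens 70 days after treatment stops, and 70 > 30, so no scheduled post-baseline test falls inside. Only unscheduled tests could.

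**5. Size.** The documents do not say what share enters above 5 x ULN. Assume 2-10%:

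- 0.02 x 125 = 2.5 and 0.10 x 125 = 12.5, so about 3-13 of the 125 in the standard arm.
- This is a ceiling under the assumption, because values that fall below 5 x ULN by week 4 drop out of the Grade 3 row.

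**The case against.** **The cut-offs are right.** The mg/dL values come first, and 43 and 51 are their correct equivalents in micromol/L. A reader might infer that the plan sets bilirubin thresholds 1000-fold too high and so will report no raised bilirubin. The documents do not support that. It would take a programmer who ignored the mg/dL value and applied an impossible limit. A micro sign lost in typesetting or file conversion is also possible: the sign appears in the Protocol exclusion criteria but nowhere in the SAP. That would not explain the g/L rows.

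**Mixed units need not be pooled.** A reader might take the baseline bilirubin row to put both units into one mean. In an unfilled shell the word *or* more naturally means that one is to be chosen. What stands is that no unit is chosen and no conversion rule is given, although tests are run at local laboratories in several countries.

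**There is a window and a baseline rule.** A reader might infer that the ALT/AST rows have no time limit and count the entry draw itself. The general safety window and the baseline definition both speak against that. What stands is narrower. The enzyme rows lack the footnote that the haemoglobin and bilirubin rows carry. The same table also reports changes at post-treatment week 12, outside the 30-day limit. Nothing requires a graded value to be worse than the participant's own baseline.

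**All 375 are not exposed.** Applying an assumed 2-10% to the whole trial would give about 8-38 participants. That figure is unsupported, because the simplified arm has no scheduled liver test in the window.

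**Baseline is not absent, and the stakes are limited.** Tables 19 to 21 give baseline values and changes, but as arm-level summaries that cannot show which graded values are new. The reference to treatment-emergent laboratory abnormalities does not promise that Table 21 counts only worsening. The SAP's primary safety endpoints include no laboratory measure. These points keep the matter minor.

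**Conclusion.** The point holds as a minor correction to the safety tables and does not touch SVR12.

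- **Certain:** the SI bilirubin label is wrong by a factor of 1000 with correct numerals beside it; the g/L labels on the ALT and AST changes are wrong; the g/L label on the bilirubin change agrees with neither unit in its baseline row; treatment-emergent laboratory abnormality is mentioned and never defined; and the ALT/AST counts have no worsening rule although entry allows up to 10 x ULN.
- **Conditional:** bilirubin would be misreported only if the label were coded literally. ALT/AST toxicity would be overstated only for participants who enter above a grade limit and remain raised at a later draw inside the window.
- **Size:** unknown. About 3-13 of 125 in the standard arm is an upper range resting on the assumed 2-10%. Because scheduled exposure is confined to that arm, any such counts would inflate the standard arm's figures rather than fall evenly.

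Whether the ALT/AST grade limits match the grading table named in the SAP cannot be checked, because its limits are not reproduced.

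**What to change.** In SAP Table 21:

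1. Change mmol/L to micromol/L in the bilirubin baseline and category rows.
2. State one reporting unit for bilirubin, convert all results to it before summarising, and give the bilirubin change in that unit.
3. Give the ALT and AST changes in U/L.
4. Count an ALT or AST grade only if the value is post-baseline, lies between first dose and 30 days after last dose, and is at least one grade above the participant's own baseline grade. Show the baseline grade as a separate row. Grades 3 and 4 must be held separately in the data, so that a participant who starts at Grade 3 can be seen to worsen.
5. Put the same rule in the Laboratory Evaluation section as the definition of a treatment-emergent laboratory abnormality.

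The cost is a set of table-shell edits and one extra derivation, with no new data. The downside is that fewer participants may be counted as Grade 3 or more. The baseline-grade row keeps those left out visible.

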# At any time during treatment and up to 30 days post; each participant should only be included once - record most severe grade of anaemia for each participant

\*At any time during treatment and up to 30 days post; add footnote, if bilirubin elevated at screening/baseline

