### **4.3 Treatment Discontinuation Criteria**

Study drug may be discontinued for reasons including, but not limited to, the following:

- AEs or laboratory abnormalities for which study drug discontinuation is deemed necessary by the Investigator and/or the Medical Monitor
- Significant protocol violation.
- Participant request to discontinue study drug or withdraw from the study for any reason.
- Discontinuation of the study by the Kirby Institute, regulatory agencies or a Human Research Ethics Committee / Research Ethics Committee / Institutional Review Board.

In the event that a positive pregnancy test result is obtained in a female participant during treatment with glecaprevir/pibrentasvir, the administration of study drug may be continued at the Principal Investigator's discretion after discussion with the participant, if the benefit of continuing study drug is felt to outweigh the potential risk.

Participants who cease study medication will, wherever possible, continue to be followed up according to the protocol study plan by completing the EoT visit at the time of treatment termination and SVR12 visit at week 20. Participants may revoke consent for follow-up without jeopardizing their relationship with either their doctor or the UNSW. If a participant wishes to withdraw from the study then, if possible, all assessments scheduled for the SVR12 (week 20) visit should be completed.

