### **End of Treatment (Week 8) – All participants**

Via phone contact 1-2 days prior to week 8. A maximum of three attempts should be made by the site personnel to contact the participant over the phone. Phone contact attempts must be within the visit window allowed per protocol. All attempts must be recorded in the source documents.

- Adverse Events
- Concomitant medication
- Adherence survey

In addition to the above the following assessments will be completed at week 8:

	Standard treatment monitoring group	Simplified treatment monitoring group
HOME	Completed at HOME by the participant: NIL	Completed at HOME by the participant: 
 
• Pregnancy test (females of child bearing potential only)
 

CLINIC	Completed at the CLINIC : 
 
• Vital signs and physical measurements
 
• HCV RNA (Local Lab.)
 
• LFTs, FBC and biochemistry (Local Lab.)
 
• Pregnancy test (females of child bearing potential only)
 
• Research specimen collection (Central Lab.): 
 
• EDTA plasma (at all sites)
 
 
 
	Completed at the CLINIC : NIL – participant is not required to attend the clinic

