#### **Unscheduled visits**

Unscheduled visits may occur for a number of reasons including, but not limited to, adverse events, early treatment discontinuation or study termination. In the event of treatment or study termination an

unscheduled visit should be performed where possible. In the event of an unscheduled visit the following data may be collected if applicable:

- Adverse Events
- Concomitant medication
- Vital signs and physical measurements
- HCV RNA and genotype (Local Lab.)
- LFTs, FBC and biochemistry (Local Lab.)
- HIV antibody & HBV serology (Local Lab.)
- Pregnancy test (females of child bearing potential only)

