## **7.0 Recording and reporting Adverse Events (AEs) and Product Complaints**

### **7.1 Definitions of Adverse Events, Adverse Reactions and Serious Adverse Events**

#### **7.1.1 Adverse Event definition**

Adverse events and adverse drug reactions may occur in the course of this study and within the specified follow-up period. These events may also occur in screened participants during the screening period prior to enrolment as a result of protocol-specified interventions. Adverse events will be collected for all participants in the clinic at baseline and SVR (week 20) visits and via phone contact at the week 4 and EoT (week 8) visits.

The definition of an adverse event is any untoward medical occurrence in a participant administered with a pharmaceutical product which does not necessarily have a causal relationship with the product.

Pre-existing conditions or diseases that occur during the study (e.g. seasonal allergies, asthma or recurrent headaches) should not be considered as adverse events unless they change in frequency or severity

All adverse events encountered during treatment and for 12 weeks after drug discontinuation must be reported on the Adverse Event Page of the electronic case report form (eCRF).

Laboratory test abnormalities (results outside the normal range) as such should not be reported as adverse events unless they result in a clinically relevant condition including but not limited to modification or discontinuation of study drug. Overdoses of study drug without clinical sequelae should not be reported as an adverse event.

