#### On-treatment

Nominal visit	Standard monitoring arm			Simplified monitoring arm		
	Nominal day	Lower Limit	Upper Limit	Nominal day	Lower Limit	Upper Limit
Baseline	1	NA	1	1	NA	1
Week 4	28	21	42	NA	NA	NA
Week 8	56	43	59	NA	NA	NA

\*The protocol specifies that the visit window for Week 4 and Week 8 is plus or minus 3 days.

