#### Post-treatment

Nominal visit	Standard monitoring arm			Simplified monitoring arm		
	Nominal day	Lower Limit	Upper Limit	Nominal day	Lower Limit	Upper Limit
PT week 12	84	70	NA	84	70	NA

\*The protocol specifies that the visit window for Post Treatment Week 12 is plus or minus 14 days. As the post treatment week 12 visit is the final scheduled study visit, the upper limit for the post-treatment week 12 visit will not be specified, and instead will be set at study close.

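### SAP Table 21 sets on-treatment haemoglobin and bilirubin abnormalities side by side by arm, although only the standard arm has scheduled blood tests in that period

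*SAP*

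**What the plan says.** SAP Table 21 (Laboratory evaluation) has one column per arm, each headed with a blank N. Two of its row groups carry a footnote that sets a time window. The haemoglobin row reads "Haemoglobin #, n (%) Grade 2 Grade 3 Grade 4", and its footnote is "At any time during treatment and up to 30 days post; each participant should only be included once", keeping the worst grade. The total bilirubin row has the same window.

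Both measurements come from the routine blood tests (Protocol 6.1): haemoglobin from the full blood count, total bilirubin from the liver function tests. The two Schedules of Assessments place these tests as follows:

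- Standard arm: screening, baseline, weeks 4, 8 and 20.
- Simplified arm: screening, baseline and week 20 only.

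For the simplified arm at weeks 4 and 8, Protocol 6.1 says the "participant is not required to attend the clinic". The SAP's on-treatment analysis-window table agrees. It prints NA for that arm at both weeks, above a note that "The protocol specifies that the visit window for Week 4 and Week 8 is plus or minus 3 days".

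Other routes to a test are open but not systematic:

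- On termination of treatment or study, an "unscheduled visit should be performed where possible" (Protocol 6.1, Unscheduled visits), with laboratory tests among the optional items.
- For a participant who withdraws, "if possible, all assessments scheduled for the SVR12 (week 20) visit should be completed" (Protocol 4.3).

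**The concern.** The trial asks whether on-treatment visits can be dropped. These are the only table rows with a stated on-treatment laboratory window, so a reader looking for laboratory harm during unmonitored treatment will go to them. An abnormality that is never looked for cannot be counted, and a low simplified-arm figure could then be taken as reassurance when it only reflects the absence of testing.

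No other output fills the gap:

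- SAP Tables 19 and 20 hold only baseline, post-treatment week 12 and the change between them.
- The adverse event tables do not capture the missing results. Protocol 7.1.1 says "Laboratory test abnormalities (results outside the normal range) as such should not be reported as adverse events", unless they result in a clinically relevant condition.

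Elsewhere the plan does guard against unequal observation. Nurse calls are made in both arms, standard-arm drug return is held back to the SVR12 visit, and SAP Table 16 separates adverse events by phone and clinic contact. Table 21 has no such safeguard.

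**Working it through.** The plan states no figure on this point. The plan figures used are the arm sizes, 125 standard and 250 simplified (Protocol 10.1), and the visit days.

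**Step 1: where the window ends.** For a last dose on day 56, the window closes at 56 + 30 = day 86. The SAP notes that "the visit window for Post Treatment Week 12 is plus or minus 14 days", so the week 20 visit falls no earlier than 140 − 14 = day 126, which is 126 − 56 = 70 days after last dose. This matches the SAP's own lower limit of 70. If the 4 spare days of supply were used (last dose day 60), the gap is 126 − 60 = 66 days, still outside the window.

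**Step 2: scheduled tests inside the window.**

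| Scheduled test | Day | Standard | Simplified | In window |
|---|---|---|---|---|
| Baseline | 0 | yes | yes | no (SAP: on or before first dose) |
| Week 4 | 28 | yes | no | yes |
| Week 8 | 56 | yes | no | yes |
| Week 20 | 140 | yes | yes | no |

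Standard: 125 × 2 = 250, if all attend. Simplified: 250 × 0 = 0. If a baseline sample on the day of first dose were counted as on treatment, the count per participant would be 3 against 1, still unequal.

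**Step 3: what each denominator does.**

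- *Arm total.* The SAP uses the safety population for all safety analyses, so this is the natural reading of the blank N. Simplified-arm participants with no test then sit in the denominator as if normal.
- *Number tested.* The SAP's Missing Data section drops a participant with a missing laboratory result from the summary for that time point. Extended to a whole window, that rule leaves only simplified-arm participants with an unscheduled, termination or withdrawal test.

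**Step 4: illustration only.** The documents give no rates, so every rate here is an assumption. Let *p* be the true share with an abnormality (equal in both arms), *s* the share of those caught by the two scheduled tests, and *q* the share caught by event-driven tests (equal in both arms). With the arm total as denominator:

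- standard = *p*[1 − (1 − *s*)(1 − *q*)]; simplified = *pq*; gap = *ps*(1 − *q*).
- *p* = 0.3%, *s* = 75%, *q* = 25%: gap 0.17 points (about 0.3 of 125 against 0.2 of 250 participants).
- *p* = 1%, *s* = 50%, *q* = 50%: 0.75% against 0.50%, gap 0.25 points.
- *p* = 3%, *s* = 75%, *q* = 25%: 2.44% against 0.75%, gap 1.69 points.
- *p* = 5%, *s* = 100%, *q* = 0: 5.0% against 0%, gap 5.0 points.

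With number tested as denominator, let *r* = 5% of normal simplified-arm participants have an unscheduled test, and treat the standard arm as fully tested. In the 3% case the number tested is 250 × (0.03 × 0.25 + 0.97 × 0.05) = 14.0, of whom 1.875 are abnormal. That is 13.4%, against 2.4% in the standard arm, so the contrast reverses. Changing the denominator alone does not make the arms comparable.

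**The case against.** The strongest reply is that no inference is planned here. SAP Tables 10 and 11 have columns for the difference and P; Table 21 has neither. The absence of on-treatment visits is the declared intervention, so an informed reader would expect it. That stands as far as it goes: the rows are descriptive. But n (%) in adjacent columns invites comparison, and Table 21 carries no warning, whereas Table 10 and the on-treatment window table print NA where the simplified arm has no visit.

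A second reply is that the missing-laboratory rule points against counting untested people as normal. This also stands in part. The rule is worded by time point, so it does not settle an any-time, worst-grade row, but neither can it be said that the SAP will use the arm total.

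A third is that abnormalities may be rare. The protocol excludes low haemoglobin and raised direct bilirubin at screening and describes drug toxicity as very low. At a 0.3% true rate both cells would most likely read zero. This limits how visible the problem might be; it does not make the columns comparable.

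Finally, Protocol 4.3 asks participants who stop early to complete the end-of-treatment visit, without distinguishing the arms. The simplified arm's week 8 clinic content is nil, but whether that carries over to early stoppers is an inference. At most it would add tests for those who stop early, who are themselves a selected group.

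**Conclusion.** The concern holds for the haemoglobin-grade and total-bilirubin-category rows of SAP Table 21. Two scheduled tests per participant against none follows directly from the schedules, and neither available denominator removes the imbalance. It should be corrected, but it is a display problem, not a flaw in the trial's main conclusions.

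Some readers might infer more than the documents support:

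- *That the simplified arm will look safer by a known amount.* The size cannot be derived. The 0.17 to 5.0 point range rests on assumed rates, and even the direction depends on the denominator and on event-driven testing catching the same share in both arms.
- *That the SAP plans a test on these rows.* SAP Table 9 lists laboratory abnormalities as a secondary endpoint, and Protocol 10.3 plans pairwise comparisons for all secondary endpoints. But the protocol's own secondary and safety endpoint lists contain no laboratory endpoint, and Table 21 has no comparison column.
- *That the safety analysis as a whole is affected.* The primary safety endpoints, the week 12 change rows and primary efficacy do not use these rows.
- *That the ALT and AST grade rows share the defect.* They carry no window footnote, so the table does not establish this.

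**What to change.** 1. Show the two windowed row groups as a summary for the standard arm only, with the number tested in the window as denominator.
2. Mark the simplified column NA, stating that this arm has no scheduled on-treatment tests, following the SAP's own practice in Table 10 and the on-treatment window table.
3. Give any abnormalities found at unscheduled, termination or withdrawal visits in the simplified arm as a count or listing with the number tested, and no percentage.
4. Add a footnote that the arms are not to be compared on these rows.
5. If a between-arm display of graded abnormalities is wanted, give it at post-treatment week 12, the only scheduled post-baseline test common to both arms. Use number tested as denominator and note that it does not measure on-treatment toxicity.

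Items 1 to 4 cost one revised table shell, a short count or listing, and a footnote. Item 5 is optional and adds one display. No new data are needed. The price is that the SAP then states openly that no on-treatment laboratory comparison between arms is available.
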